## Abstract

**Background:** Studies have revealed that time-restricted feeding affects the fat oxidation rate; however, its effects on the fat oxidation rate and hyperlipidemia following high-fat meals are unclear. This study investigated the effects of 5-day time-restricted feeding on the fat oxidation rate and postprandial lipemia following high fat meals. **Methods:** In this random crossover experimental study, eight healthy male adults were included each in the 5-day time-restricted feeding trial and the control trial. The meals of the time-restricted feeding trial were provided at 12:00, 16:00, and 20:00. The meals of the control trial were provided at 08:00, 14:00, and 20:00. The contents of the meals of both trials were the same, and the calories of the meals met the 24-hour energy requirement of the participants. After 5 days of the intervention, the participants consumed high-fat meals on the sixth day, and their physiological changes were determined.

**Key words:** intermittent fasting, oral fat tolerance test, fat oxidation

## Introduction

Consuming high-fat meals increases the triglyceride (TG) level in blood plasma. Studies have discovered that large increases in postprandial TG concentration lead to high risks of cardiovascular diseases and metabolic syndrome . Compared with the fasting TG concentration, the postprandial TG concentration is a more precise predictor of the risks of cardiovascular diseases and metabolic syndrome . Consuming high-fat meals increases the levels of biochemical substances in blood plasma, such as TG, free fatty acids, and remnant cholesterol. Studies have reported that these biochemical substances are major risk factors for metabolic syndrome, atherosclerosis, myocardial infarction, and coronary heart disease, all of which are associated with high mortality . The high TG level after the consumption of high-fat meals can last for 6–8 hours. As three meals daily are typically consumed by the general population, high levels of TG may be constantly occurring in the body. Therefore, investigating methods to reduce the high TG level after eating high-fat meals is crucial for reducing the development of metabolic syndrome.

Studies have demonstrated that a single session of endurance exercise can effectively reduce the TG level after the consumption of high-fat meals . In addition, performing a single session of endurance exercise 8 hours before meals can effectively reduce the increase in TG after the consumption of high-fat meals, and the effect can last for 48–60 hours . Endurance exercises effectively reduce the increase in postprandial TG because they increase lipoprotein lipase activity and insulin sensitivity, and they reduce the release of very low-density lipoprotein by the liver . Recent studies have shown that increasing the fat oxidation rate after eating high-fat meals is crucial for reducing the postprandial TG level ; however, the results have remained inconsistent. Some studies have described that performing high-intensity interval

training is positively correlated with decreases in the postprandial TG level , whereas other studies have discovered that the increased fat oxidation rate following high-fat meals did not affect the postprandial TG level .

Studies have discovered that time-restricted feeding can improve insulin sensitivity , increase the fat oxidation rate , and decrease the fasting TG level . However, whether time-restricted feeding can exert health benefits in terms of effectively reducing the increase in the TG level following high-fat meals remains unclear. This study investigated the effects of 5-day time-restricted feeding on the fat oxidation rate and postprandial lipemia after the consumption of high-fat meals.

## Methods

### Participants

This study recruited eight healthy male adults as research participants (age:  $22 \pm 1.3$  yr, height:  $170.1 \pm 4.7$  cm, weight:  $75.4 \pm 17.5$  kg). All the participants had not undergone physical training; they did not exercise regularly; and they did not have any diseases that would prevent them from performing exercises, such as high blood pressure, hyperlipidemia, heart disease, joint disease, and osteoporosis. All the participants fully understood the experimental process before experiment initiation and were notified of the possible risks; they agreed to the terms of the experiment and provided their written consent. A similar number of participants and a similar

recruitment method have been employed by this research team in the past. This study was approved by the Institutional Review Board of Jen-Ai Hospital (110-10) in Taiwan.

## Design

This study used a crossover design for the experiment. The participants were divided into the time-restricted feeding trial and the control trial; the participants in the control trial did not practice intermittent fasting methods. The participants of both trials consumed the same meals for 5 days. The time-restricted feeding group used the 16:8 methods to practice intermittent fasting. The meals were provided at 12:00, 16:00, and 20:00. The meals of the control group were provided at 08:00, 14:00, and 20:00, but the consumption time was not limited. On the morning of the sixth day, all participants returned to the laboratory to consume high-fat meals, and their TG blood levels after the meal was determined. The participants were randomly assigned to different arms of the study to receive different treatments, and an interval of at least 14 days was maintained between the tests to avoid any effects of the preceding test on the succeeding test. Studies have discovered that 4 days of intermittent fasting effectively increased the fat oxidation rate and reduced blood glucose . Therefore, 5 days of intermittent fasting should provide sufficient intervention time to stimulate fat oxidation rate changes.

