### Formal Experiment

The experiment was conducted over 6 days. On the first day, the participants arrived at the laboratory at 08:00 and quietly rested for 20 minutes in the supine position; gas analyzers were used to record their energy consumption. Subsequently, the participants were randomly allocated to the time-restricted feeding trial or the control trial. The meals of the time-restricted feeding trial were provided at 12:00, 16:00, and 20:00, and the participants were required to consume all the food during this time. The meals of the control trial were provided at 08:00, 14:00, and 20:00, but the consumption

time was not limited. In addition to regular meals, a snack with approximately 200 calories was provided to the participants for consumption. The participants in the time-restricted feeding trial were only allowed to consume the snack from 12:00 to 20:00, whereas no restrictions were imposed on the control trial for snack consumption. The meals of the participants were provided by dieticians. Based on the results of the pretest, the calories of each meal met the daily energy requirement of the participants. The macronutrient consumption for TRF and CON were listed in table 1.

After experiment completion on the fifth day, the participants returned to the laboratory on the eighth day from 08:00 to 09:00. They rested for 10 minutes in the supine position, and gas analyzers were used to collect the gas data of the participants for 20 minutes. Next, a catheter was inserted into the forearm of each participant to collect fasting blood samples. After blood sample collection, the participants were provided with a specific high-fat meal. The participants rested quietly in the laboratory for 4 hours, and their blood lipid changes during this period were observed.

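### Control eating times are left free on the evening before a sample labelled fasting, so length of fast may differ by condition in the fasting comparisons

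*Protocol*

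**What the plan says.** The evening rule differs between the two conditions.

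- **Control.** Design says: "The meals of the control group were provided at 08:00, 14:00, and 20:00, but the consumption time was not limited". Formal Experiment repeats this and adds, for the snack of about 200 calories, "whereas no restrictions were imposed on the control trial for snack consumption".
- **Time-restricted feeding.** Design says "The time-restricted feeding group used the 16:8 methods to practice intermittent fasting", with meals handed out at 12:00, 16:00 and 20:00. Formal Experiment adds that "the participants were required to consume all the food during this time" and that "The participants in the time-restricted feeding trial were only allowed to consume the snack from 12:00 to 20:00". The last meal is handed out at the moment the window closes, and no finishing time is given.

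On the test morning (Formal Experiment), participants arrive between 08:00 and 09:00, rest for 10 minutes, have gas collected for 20 minutes and then give a blood sample described as fasting. Statistical Analysis compares fasting fat oxidation between conditions by paired t test. Blood biochemical values stand in the same sentence, and it is not clear whether the word fasting covers them too. No section gives a length of fast, a common last intake or a check of last intake.

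The test day itself is stated in two ways. The Abstract says "the participants consumed high-fat meals on the sixth day", Design says "On the morning of the sixth day, all participants returned to the laboratory to consume high-fat meals", and Formal Experiment opens with "The experiment was conducted over 6 days". A later sentence in Formal Experiment puts the return visit on the eighth day.

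**The concern.** The fasting comparisons are meant to show what five days of time-restricted feeding do to resting metabolism. That requires the two test mornings to differ in the preceding five days and not also in how long ago the participant last ate. As written, a control participant may eat the 20:00 meal or the snack late in the evening and still comply, whereas a time-restricted participant may not take the snack after 20:00.

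A difference of this kind would arise within each participant and go with condition. Pairing removes stable differences between people, and random order balances period effects. Neither removes something that travels with the condition. The effect of the last night's fast could then not be separated from that of the 5-day intervention.

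The exposed comparisons are fasting fat oxidation and, if the word fasting in Statistical Analysis extends to the blood values, up to five plasma measures: triglyceride, glucose, free fatty acid, glycerol and insulin.

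**Working it through.** **Inputs from the Protocol.** Last meal handed out at 20:00 in both conditions; first meal at 12:00 (restricted) or 08:00 (control); arrival 08:00–09:00; 10 minutes' rest, then 20 minutes' gas collection, then blood.

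**Inputs assumed.** Control last intake at 22:00 or 24:00, and restricted meal finished at 20:30. The Protocol gives none of these times; they only show the range.

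**1. The plan's own schedule.** The restricted window runs from 12:00 to 20:00 = 8 h, and the overnight fast from 20:00 to 12:00 = 16 h, which reproduces the stated 16:8. The control overnight fast is 20:00 to 08:00 = 12 h. The scheduled contrast is 16 − 12 = 4 h.

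**2. How much of that contrast is present at the test.** The 4 h lie between 08:00 and 12:00. Participants arrive at 08:00–09:00, when both conditions are nominally 12–13 h from 20:00. So 0 of the 4 h falls before 08:00, and the scheduled gap at the test is 0 h. Any real gap must come from intake after 20:00, not from the meal timetable.

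**3. Nominal fast at each measure, counted from 20:00.**
- Gas collection starts at arrival + 10 min: 12.17–13.17 h.
- Blood is drawn at the earliest at arrival + 30 min: 12.5–13.5 h.

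**4. Gap if the restricted condition stops at 20:00.** Gap = control last intake − 20:00; share = gap ÷ nominal fast.

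| Control last intake (assumed) | Gap | Share at gas | Share at blood |
|---|---|---|---|
| 20:00 | 0 h | 0% | 0% |
| 22:00 | 2 h | 2/13.17 = 15.2% to 2/12.17 = 16.4% | 2/13.5 = 14.8% to 2/12.5 = 16.0% |
| 24:00 | 4 h | 4/13.17 = 30.4% to 4/12.17 = 32.9% | 4/13.5 = 29.6% to 4/12.5 = 32.0% |

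**5. Gap if the restricted condition finishes its meal at 20:30.** Its fast at the blood sample is then 12.0–13.0 h.
- Control at 22:00: gap 1.5 h; 1.5/13 = 11.5% to 1.5/12 = 12.5%.
- Control at 24:00: gap 3.5 h; 3.5/13 = 26.9% to 3.5/12 = 29.2%.
- Control at 20:00: gap 20:00 − 20:30 = −0.5 h, so the restricted fast is the shorter one. The rule therefore lets mainly, but not only, the control condition shorten its fast.

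**6. Dependence on the test day.** Steps 2 to 5 take the test as the morning after day 5, in line with the Abstract, Design and the opening of Formal Experiment. If the test is on the eighth day, no section describes intake after day 5 in either condition. Fast length is then uncontrolled in both conditions but not tied to treatment.

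These shares describe hours of fasting. The Protocol gives nothing that would convert them into a shift in any outcome, so no such conversion is made.

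**The case against.** The strongest reply has four parts.

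**The timetable is balanced.** Both last meals come at 20:00 and both conditions share one arrival window, so the plan gives equal nominal fasts. Every non-zero gap above rests on an assumed intake time. This stands as a limit on size. It does not settle the point, because the time a meal is handed out is not the time it is eaten, and the Protocol expressly frees the latter for controls.

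**Free timing is the comparator.** The control condition is defined by not practising intermittent fasting, so a participant who eats late is following the assignment, and a shorter fast may be part of the intended contrast. This is a fair reading. The Protocol does not say whether it is the one meant, and the interpretation of the fasting results turns on it.

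**The wording may mean duration.** Unlimited consumption time could mean that no limit was put on how long each meal took, as opposed to the 15 minutes allowed for the test meal. This is possible but the weaker reading, since Formal Experiment sets the phrase against the restricted condition's feeding times. On either reading the control snack remains unrestricted.

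**Only part of the analysis is exposed.** The main aim concerns responses after the high-fat meal, and what is at risk is the fasting comparisons. This stands. Fasting fat oxidation is nonetheless a named comparison in Statistical Analysis.

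**Conclusion.** The concern holds and should be fixed; confidence is medium. It is certain from the text that the evening rule is unequal and that no fast length or last-intake check precedes the measures labelled fasting. On the sixth-day reading, any resulting gap would go with condition and survive both pairing and randomised order.

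Its size is not known. The scheduled gap is 0 h. Under the assumed intake times it ranges from 1.5 to 4 h, about 12% to 33% of the fast. Nothing in the Protocol shows that late eating took place. On the eighth-day reading, the link to condition disappears and a general lack of control over intake takes its place.

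**What to change.** For the evening before the test only, apply the same last-intake time and the same minimum fast to both conditions, with the length for the investigators to set. Record the time of last intake and confirm it at the test visit. Control timing can stay free on the earlier days, so the comparator is otherwise unchanged. If a shorter control fast is meant to be part of the contrast, the Protocol should say so. The sixth-day and eighth-day statements must be reconciled.

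If the data are already collected, report any last-intake times that are held. If none are, state that fast length was uncontrolled and limit the interpretation of the fasting comparisons accordingly.

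The cost is one instruction and one recorded time per test visit, plus one text correction. The small downside is that the control condition is slightly less free-living on one evening.

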## Protocol

### Pretest

In the pretest, gas analyzers (Vmax Series 29C, Sensor Medics, CA, USA) were used to assess the energy consumption of the participants while they were resting and performing nonmaximal intensity exercises for precisely calculating the daily calorie consumption of each participant. After the participants arrived at the laboratory, they wore heart rate monitors (Polar, Finland), and their energy consumption was examined using gas analyzers. Next, they quietly rested for 20 minutes in the supine position, and their resting heart rate and energy consumption were recorded. They then performed nonmaximal intensity exercises for measuring their energy consumption during low-intensity activities. The participants stood on a treadmill with a slope of 0° for 10 minutes to record their energy consumption during standing. The participants then walked or ran on the treadmill at five speeds, namely 1, 2, 3, 4, and 5 miles per hour. The participants maintained each speed for 3 minutes for examining the relationship between the energy consumption and heart rate of the participants during low-intensity activities.

After the pretest, the participants were asked to perform their normal daily life activities while wearing the heart rate monitor; their heart rates were recorded for 24

hours. The 24-hour heart rate, the regression curve of the heart rate, and energy consumption calculated in the pretest were used to calculate the total energy consumption of the participants. In the experiment, meals were adjusted so that the total calories of each meal met the 24-hour energy requirement of each participant. The method used to record energy consumption and the brand of heart rate monitors (Polar) used in this study have been described elsewhere . Moreover, 24-hour energy consumption was recorded the day before the experiment, and the calories of meals were adjusted to meet the 24-hour energy requirement of each patient. The same methods were repeated on the fifth day of the experiment to confirm the 24-hour energy consumption changes of the two trials.

### Formal Experiment

The experiment was conducted over 6 days. On the first day, the participants arrived at the laboratory at 08:00 and quietly rested for 20 minutes in the supine position; gas analyzers were used to record their energy consumption. Subsequently, the participants were randomly allocated to the time-restricted feeding trial or the control trial. The meals of the time-restricted feeding trial were provided at 12:00, 16:00, and 20:00, and the participants were required to consume all the food during this time. The meals of the control trial were provided at 08:00, 14:00, and 20:00, but the consumption

time was not limited. In addition to regular meals, a snack with approximately 200 calories was provided to the participants for consumption. The participants in the time-restricted feeding trial were only allowed to consume the snack from 12:00 to 20:00, whereas no restrictions were imposed on the control trial for snack consumption. The meals of the participants were provided by dieticians. Based on the results of the pretest, the calories of each meal met the daily energy requirement of the participants. The macronutrient consumption for TRF and CON were listed in table 1.

After experiment completion on the fifth day, the participants returned to the laboratory on the eighth day from 08:00 to 09:00. They rested for 10 minutes in the supine position, and gas analyzers were used to collect the gas data of the participants for 20 minutes. Next, a catheter was inserted into the forearm of each participant to collect fasting blood samples. After blood sample collection, the participants were provided with a specific high-fat meal. The participants rested quietly in the laboratory for 4 hours, and their blood lipid changes during this period were observed.

#### Oral fat tolerance test (OFTT)

All oral fat tolerance test (OFTT) meals were designed and provided by dieticians, as previously described . The meals included toast, butter, cheese, muesli, and

cream. For every kg of the body weight of the participant, the meal provided 1.2 g of fat, 1.1 g of carbohydrate, 0.33 g of protein, and 16.5 kcal of energy. The nutritional information was obtained from the nutritional facts on food packages. During the experiment, the participants were required to consume the OFTT meal within 15 minutes.

#### Blood collection

In the experiment, a catheter (Venflon 20G, Sweden) was inserted into the vein of the forearm, and a three-way stopcock (Connecta Ltd., Sweden) was used to collect 10 mL of blood each time. Blood was collected before meals, 30 minutes after meals, and every hour after meals up to the fourth hour. After each session of blood collection, 10 mL of isotonic saline water was used to clean the catheter to avoid blood clotting in the catheter.

The collected blood was immediately placed in blood collection tubes containing ethylenediaminetetraacetic acid. A cell counter was used to analyze the hematocrit (Sysmax KX-21N, Kobe, Japan). After the analysis, the blood was centrifuged for 20 minutes at  $500 \times g$  at 4°C. Blood plasma was obtained and was immediately placed in a -80°C refrigerator for preservation and future biochemical analysis.

#### Blood biochemical analysis

TG, blood glucose, free fatty acid, and glycerol levels in blood were analyzed using an automated biochemistry analyzer (7020, Hitachi, Japan) and commercial reagents (GOD-PAP method, Randox, Ireland). The insulin concentration in blood plasma was analyzed using a chemiluminescence immunoassay analyzer (Elecsys 2010, Roche Diagnostics, Basel, Switzerland) and commercial reagents (Roche Diagnostics). The fat and carbohydrate oxidation rates were calculated using the following formula:

$$\text{Fat oxidation (g/min)} = 1.695 \times \text{VO}_2 - 1.701 \times \text{VCO}_2$$

$$\text{Carbohydrate oxidation (g/min)} = 4.585 \times \text{VCO}_2 - 3.226 \times \text{VO}_2$$

### Statistical Analysis

All the data in this study are presented as average  $\pm$  standard deviation. First, the normality of the data was tested using the Shapiro–Wilk test. The fasting fat oxidation rate, blood biochemical values, and areas under the fat oxidation rate curve and the TG curve were analyzed using the paired sample t test. The postprandial fat oxidation rate and blood biochemical values were analyzed using two-way ANOVA with repeated measures. If the data were significant, the Bonferroni method was used to perform post hoc comparisons. Using G\*power 3, to achieve an alpha value of 5% and a power of 0.8, the sample size of eight was considered sufficient for this study. The significance level was set at  $\alpha < 0.05$ .

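### Holm's step-down method would serve the post hoc comparisons better than single-step Bonferroni: same nominal 5% family-wise error, never fewer rejections, and a gain that depends on how many sampling times differ

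*Protocol*

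**What the plan says.** The Statistical Analysis section of the protocol sets out two routes. Fasting values and areas under the curve are compared by paired t test. For the time course, "The postprandial fat oxidation rate and blood biochemical values were analyzed using two-way ANOVA with repeated measures", followed by: "If the data were significant, the Bonferroni method was used to perform post hoc comparisons".

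The Blood collection section fixes the blood sampling times: "Blood was collected before meals, 30 minutes after meals, and every hour after meals up to the fourth hour". That makes six samples per visit, at 0, 0.5, 1, 2, 3 and 4 hours.

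The Design section states "This study used a crossover design for the experiment", and Participants gives eight men. A comparison of the two trials at one sampling time is therefore paired, with 7 degrees of freedom.

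The only statement on power is "to achieve an alpha value of 5% and a power of 0.8, the sample size of eight was considered sufficient for this study". It comes without an effect size, an endpoint or a test.

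**The concern.** The post hoc step is the only planned analysis that can show when after the meal the two trials differ; the areas under the curve cannot. With eight men, a single-step Bonferroni correction over six times raises the required |t| from 2.36 to 3.64 at every time, including times tested after others have already been declared different. Holm relaxes the threshold after each rejection at the same nominal family-wise level. What is at stake is power to identify further differing times, in a trial with little power to spare.

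**Working it through.** **1. Inputs**
- From the protocol: n = 8, paired (Participants, Design); alpha 5% and power 0.8 (Statistical Analysis); six blood samples (Blood collection); Bonferroni (Statistical Analysis).
- Assumed, because not stated: two-sided tests; each post hoc comparison a paired t test on 7 df; standardised paired effect dz; number k of times that truly differ; correlation rho between the paired differences at different times.

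**2. The plan's own figure**

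n = 8 cannot be reproduced without an effect size, so it is solved backwards. For a two-sided paired t test,

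power = P(|T| > t crit), T noncentral t on 7 df with noncentrality dz × √8.

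At alpha 0.05, t crit = 2.365. Power 0.80 requires dz = 1.156 (noncentrality 1.156 × 2.828 = 3.27). This is a working assumption about effect size, not a figure from the protocol.

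**3. Bonferroni over six times**

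Threshold 0.05/6 = 0.00833; t crit = 3.636. At dz = 1.156, power at a single time falls from 0.800 to 0.438.

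**4. Why Holm dominates**

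Order the p values p(1) ≤ … ≤ p(6) and reject in turn while p(i) ≤ 0.05/(6 − i + 1). The thresholds are 0.0083, 0.0100, 0.0125, 0.0167, 0.0250 and 0.0500.
- None is below 0.0083, so every Bonferroni rejection is also a Holm rejection.
- If m0 hypotheses are true, the first true one to be rejected must have p ≤ 0.05/m0. The chance that any of the m0 does so is at most m0 × 0.05/m0 = 0.05, whatever the correlation.

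**5. Size of the gain**

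Simulation with 40,000 trials per row, n = 8, dz = 1.156, six times, equal correlation 0.5, no ANOVA gate. Power is the average over the truly affected times.

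| Times that differ | Bonferroni % | Holm % | Gain, points |
|---|---|---|---|
| 1 | 44.1 | 44.2 | 0.1 |
| 2 | 43.9 | 45.8 | 1.9 |
| 3 | 44.1 | 48.0 | 3.9 |
| 4 | 43.7 | 50.1 | 6.3 |
| 5 | 43.9 | 53.5 | 9.6 |
| 6 | 43.8 | 58.2 | 14.4 |

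(Gains are computed before rounding.)

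**6. Sensitivity**
- Correlation 0.9, all six times affected: gain about 11 points.
- dz = 0.8: 0.1 to about 6 points.
- dz = 1.5: 0.1 to about 16 points at correlations of 0.5 and 0.8; up to about 20 over correlations from 0 to 0.9.
- Family of five (fasting sample left out), dz = 1.156, rho 0.5: 0.1, 2.4, 5.1, 8.8 and 13.8 points for one to five affected times.
- Chance of detecting at least one affected time: changes by at most about 0.2 points, because Holm's first step is the Bonferroni test.
- Realised family-wise error, five of six times affected, rho 0.5: 0.8% for Bonferroni, 2.7% for Holm. Holm stayed below 5% in every scenario with a true null.

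**7. Effect of the ANOVA gate** (dz = 1.156, rho 0.5)

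If the step runs only after a significant trial-by-time interaction, a uniform effect at all six times triggers it in about 2% of trials, and the 14.4-point gain shrinks to 0.3. The largest gated gain is then 7.5 points, with five times affected. If either a trial effect or an interaction opens the step, the gains of 9.6 and 14.4 points are kept.

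**The case against.** Bonferroni is a valid, conservative choice. It controls family-wise error under any dependence, and it has simple matching simultaneous confidence intervals, which Holm lacks. It also spends less of the error allowance in practice (0.8% against 2.7% in the case above). The areas under the curve are tested separately and are unaffected. All of this stands, which is why the point is an efficiency gain and not an error.

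A reader might go further in three ways that the protocol does not support.
- **A fixed loss of 4 to 14 points.** That range needs dz near 1.16, six comparisons, three or more affected times, and no interaction-only gate. The protocol fixes none of these except the six blood samples. With one or two affected times the gain is under 2 points.
- **A family of all 66 pairs of the 12 trial-by-time cells, with power near 11%.** The protocol states no such family. Which comparisons form the family, and which ANOVA effect opens the step, are details that a SAP may settle; their absence is not a finding.
- **Six comparisons for every outcome.** Six times are documented for blood only. The ANOVA is described for postprandial values and fasting values have their own t test, so the family may be five.

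What the objection does not remove is the dominance: for adjusted p values at the same nominal level, Holm never rejects less.

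**Conclusion.** The point holds as a cheap improvement. The protocol actively names single-step Bonferroni, and a uniformly more powerful method with the same nominal 5% guarantee is available at no cost in participants or samples. Under two-sided paired t tests, dz about 1.16 and six times, the gain is about 0 to 2 points for one or two differing times and about 4 to 14 for three to six. Across dz 0.8 to 1.5 it is roughly 0 to 16 points at correlations of 0.5 and 0.8, or about 0 to 20 more widely.

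It would be wrong to infer that the present method invalidates any result, or that Holm makes the trial more likely to find some difference. It helps only to show how many of the sampling times differ once one has been found.

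**What to change.** Replace the Bonferroni sentence with, for example: *If the ANOVA shows a significant trial effect or trial-by-time interaction, time-restricted feeding is compared with control at each sampling time by paired test, using Holm-adjusted p values over these between-trial comparisons.* State whether the fasting sample belongs to the family (six comparisons) or is tested separately (five).

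The step should not depend on the interaction alone, since that would suppress it when the effect is uniform over time.

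The cost is one sentence. Because Holm has no simple matching simultaneous intervals, report unadjusted 95% intervals beside the adjusted p values and label them as unadjusted.
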